# Responding to Elder Abuse in GERiAtric Care: Educational Intervention (REAGERA edu)

## Background and rationale for study

The prevalence of elder abuse has been reported between 10-15% in international studies (Acierno et al., 2010; Pillemer, Burnes, Riffin, & Lachs, 2016; Yon, Mikton, Gassoumis, & Wilber, 2019; Yon, Mikton, Gassoumis, & Wilber, 2017). Elder abuse may include both physical, emotional, sexual and financial abuse as well as neglect and it occurs at the hand of both professionals and family members, including adult children and intimate partners. Elder abuse has been associated with psychological ill-health, disability, increased hospitalization, emergency department use and admission to nursing facilities (X. Dong, Chen, Chang, & Simon, 2013; X. Q. Dong, 2015; Fisher, Zink, & Regan, 2011; Schofield, Powers, & Loxton, 2013). Elder abuse is however often unknown to health care providers. Older adults are hesitant to disclose abuse and health care providers are often reluctant to ask questions. In this study we will use an interactive educational model consisting of theoretical lectures, as well as group discussions and forum theatre, a form of participatory theatre (Boal, 2000; Byréus, 2010). Both group discussions and forum theatre will be using case scenarios as a cornerstone.

In forum theatre the spectators are not only observers but rather spect-actors urged to participate in the scene. The forum theatre will start with the participants own experiences of meeting with patients as well as pre-constructed cases. The actors will act out each scene, showing for example a health care professional asking an older adult about abusive experiences in a suboptimal way. Participants are invited to at any time pause the scene and suggest alternative ways of acting. They are also encouraged to take the place of one of the actors, testing the consequences of another way of acting. In this way, participants are together exploring how their action may improve the health care encounter for abused older adults.

Figure 1 is an illustration of how learning activities during the education day is related to learning objectives and study outcome measures. The figure is replicated from a published study protocol (Ludvigsson, Motamed, Westerlind, Swahnberg, & Simmons, 2022), which also describes in more details the theoretical assumption for the study as well as the content of the education. The description of study design and the planned statistical analyses that now will follow are at large part taken from that same publication (Ludvigsson et al., 2022).

## Aim:

- 1) Investigate whether the education increases participants' propensity to ask questions about abuse.
- 2) Investigate whether the education affects participants' perceived barriers to asking questions, i.e., a) awareness and sense of responsibility to care for victims of abuse b) perceived ability to ask questions about abuse c) perceived preparedness to manage cases of elder abuse and d) perceived preparedness at the clinic to care for older adults subjected to abuse.

## Study design:

The design is a non-randomised stepped wedge trial, a type of controlled cluster cohort study in which the participants gradually move from control group to intervention group (Brown & Lilford, 2006; Copas et al., 2015). In this study, a cluster entail a whole clinic or a unit at a clinic and at the end of the study all clusters will have completed the intervention, i.e., participated in the education. Data will be collected for all participants both pre- and post-intervention. Figure 2 illustrates the study design, including time plan. The intervention was originally planned to be rolled out during four periods between September 2021 and June 2023 (figure 2) and an incomplete design was chosen, i.e., six periods are used, but every cluster is only included at four measurement points: at baseline, in conjunction with the education, at six months follow up and at twelve months follow up. Similar incomplete designs have been described previously (Copas et al., 2015; Karla Hemming, Lilford, & Girling, 2015). For practical reasons the primary care centres included in the first study period had to be included later than the hospital clinics, i.e., in December 2021. To avoid a data collection period during the summer vacation, their first follow up was conducted nine months post intervention. Thereafter they will fall into the same pattern of data collection at six months interval as the other clinics. The six months interval was chosen because it provides an intermediate (six months) and long-term (twelve months) follow up that allows for a reasonable evaluation of the effect of the education. The times of data collection is illustrated in figure 2.

One geriatric clinic (cluster 8) and one primary health care centres (cluster 9) who were included at baseline decided in 2023 not to participate in the study for logistic reasons, e.g., having to prioritize other training for the staff. Therefor another primary health care centre was included (new cluster 8) and one training day was also open to participants from various primary health care centres (new cluster 9). For these clusters there is therefore no baseline data available, only pre-intervention data. In addition, the data collection phase had to be prolonged until September 2023.

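### Does a data collection end in September 2023 cut off the twelve-month follow-up, and does it matter that two sections number the replaced clusters differently?

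*Combined protocol and SAP*

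**What the plan says.** The Study design section sets out the timetable in four statements.

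- On coverage: "Data will be collected for all participants both pre- and post-intervention".
- On roll-out: "The intervention was originally planned to be rolled out during four periods between September 2021 and June 2023".
- On measurement, each cluster is seen "at baseline, in conjunction with the education, at six months follow up and at twelve months follow up". Six periods are used in all, and the Figure 2 caption gives the two follow-up windows as 6–8 and 12–14 months.
- On the late changes: "One geriatric clinic (cluster 8) and one primary health care centres (cluster 9) who were included at baseline decided in 2023 not to participate". It continues "Therefor another primary health care centre was included (new cluster 8"), with an open training day forming the new cluster 9, and then "For these clusters there is therefore no baseline data available, only pre-intervention data". The next sentence is "In addition, the data collection phase had to be prolonged until September 2023".

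The note under Figure 2 tells the replacement story with other numbers. There the geriatric clinic was to be cluster 6 and is replaced by a new cluster 6. Cluster 9 is replaced as in Study design. Cluster 8 is a separate case: a primary care centre planned at 60 participants, where seven registered.

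The Statistical analysis section pools measurements before the education against measurements after it, across clusters, in mixed models with cluster as a random effect and intervention status and time as fixed effects. Medical-record counts are to be drawn up to twelve months after the intervention.

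**The concern.** The plan calls twelve months its long-term follow-up. If collection really stopped in September 2023, clusters trained in 2023 could supply no twelve-month survey and only part of the 6–12 month record window. Those trained after March 2023 would lack the six-month survey too. The late clusters would then add little or nothing after the intervention, and the long-term conclusions would rest on the earlier clusters alone.

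The label conflict raises a second worry. The replaced clusters have no baseline survey, and the plan foresees a missing-data analysis and possibly multiple imputation. An analyst relying on the text alone could assign the absent baseline to the wrong cluster, or treat a survey that was never held as non-response.

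**Working it through.** **End date.** Inputs from Study design: roll-out planned to June 2023, last survey at 12 months, withdrawals in 2023, stated end September 2023. Input from the Figure 2 caption: upper edge of the last window, 14 months.

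1. End implied by the original plan: June 2023 + 12 months = June 2024; + 14 months = August 2024.
2. Latest training that fits a twelve-month survey under a September 2023 stop: September 2023 − 12 months = September 2022. For a six-month survey: September 2023 − 6 months = March 2023.
3. Replacements under that stop: the earliest conceivable training date is 1 January 2023, and 1 January to 30 September 2023 is 272 days, about 8.9 months. No training date in 2023 leaves room for twelve months.
4. Stated date against the implied end: June 2024 − September 2023 = 9 months. The supposedly prolonged date comes nine months before the original finish.
5. Stated date against the only earlier end date in the section: September 2023 − June 2023 = 3 months later.

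Steps 2 and 3 confirm the arithmetic of the worry. Step 4 shows that its premise fails, because a phase cannot be lengthened to a date before its planned end. Step 5 gives a reading under which the sentence makes sense: education, and the pre-intervention surveys held with it, ran three months past the planned roll-out. Twelve-month follow-up would then end between September 2024 (+12) and November 2024 (+14).

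The period count points the same way. Four roll-out periods plus two follow-up periods for the last cluster make 4 + 2 = 6, the number the plan states. If the periods are assumed to be evenly spaced at six months from September 2021, they fall in September 2021, March 2022, September 2022, March 2023, September 2023 and March 2024. The fourth lies inside the planned roll-out and the sixth lies beyond September 2023, so follow-up after that date was always part of the design.

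**Cluster numbers.**

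| | Study design | Note to Figure 2 |
|---|---|---|
| Withdrawn geriatric clinic | cluster 8 | cluster 6 |
| Its replacement | new cluster 8 | new cluster 6 |
| Withdrawn primary care centre | cluster 9 | cluster 9 |
| Cluster 8 | replaced | primary care centre, 60 planned, seven registered |

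Of the three numbers involved (6, 8, 9), only 9 agrees. For the model this has no effect: exchanging the names of two levels of a random effect leaves the likelihood, the intervention estimate and its standard error unchanged. For the missing baseline, the data set itself shows which clusters have no records in the baseline period, and Study design already explains why. The Eligibility section also admits participants who did not answer the baseline survey, so the analysis already has to accommodate people without that measurement.

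**A related slip.** Eligibility places the education of cluster 4 at step 3 and then at step 2. The note to Figure 2 says period 3, which settles it.

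**The case for a change.** The best case for a change is that the sentence refers to data collection, not education, and that no passage gives a last education date or a final survey date. Readers must therefore infer the follow-up horizon of a trial whose long-term claim depends on it. One clause would remove the doubt. The two accounts of the replacements also cannot both be right as printed, and the plan's missing-data work needs to know which clusters had no baseline by design.

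Some of this stands. The sentence is loosely worded, the 6-versus-8 conflict is genuine, and both deserve tidying if the document is reissued. But the sentence is a past-tense record of what happened, not a stopping rule. The operative rule is the four measurement points per cluster, and nothing withdraws it. Study design also sends the reader to Figure 2 for the time plan. That image was not available for this review and may settle the date. The baseline risk assumes that the people who ran the surveys would not know where they held one.

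Even if the hard stop were true, the primary comparison pools all post-intervention data and has no separate twelve-month primary endpoint. The mixed model would still use whatever surveys exist. The loss would fall on long-term conclusions for the late clusters and would be visible in the reported numbers at each time point.

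**Conclusion.** No change to the plan follows. The end date is ambiguous wording or a slip: the literal reading falls nine months short of the finish the original schedule already required, while a three-month extension of education and pre-intervention collection fits the context. The cluster numbering is a clerical conflict over one clinic and has no effect on the estimates. No cluster, participant or measurement is shown to be lost, and no effect on power is established.

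This rests on two assumptions. The first is that the four-point measurement schedule remained in force for the late clusters, which nothing in the text contradicts apart from a literal reading of this one sentence. The second is that the investigators identify the clusters without a baseline from their own survey records. If September 2023 did prove to be a true stop, the twelve-month results would cover only clusters trained by September 2022 and would have to be reported in those terms.

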## Measurements:

Self-reported measurements will be collected with the questionnaire REAGERA-P, which has previously been validated in a Swedish health care professional sample (J. Simmons, Wenemark, & Ludvigsson, 2021).

**Main outcome:** Potential effect of the training on participants asking older patients questions about abuse. This will be measured as self-reported number of times the professional has asked patients questions about abuse (range 0-10 and above). The answers will be analysed both as a dichotomous variable (never/ one or more times) and as a continuous variable.

**Secondary outcomes:** Secondary outcome measures are items in REAGERA-P about the four main learning objectives of the education (figure 1). Changes in all variables between the measurement points will be considered.

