### **Sample size**

Cluster sample size was calculated using the Shiny CRT Calculator web application (Karla Hemming, Kasza, Hooper, Forbes, & Taljaard, 2020). Significance level was set to 0.05 and power to 0.8. We planned for a three-step intervention and used the discrete time decay. Initially we had planned a complete four period stepped wedge design and hence, that was used in the sample size calculation together with the discrete time decay. Divergent cluster sizes were expected and coefficient of variation for a cluster size was set at 0.5. Results from a pilot study (Johanna Simmons, Motamed, Ludvigsson, & Swahnberg, 2022) was used to estimate cluster auto correlation at 0.6. Proportion

was set as outcome, and we used data from the pilot study to estimate the proportion under control at 0.26 and the proportion under intervention at 0.56. A cluster size of 10 then suffice to reach adequate power. Our smallest expected cluster has 31 participants and hence even with a response rate of less than 40% this is sufficient.

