## Statistical analysis

The background characteristics of participants will be explored using descriptive statistics and comparisons will be made between clusters to detect significant differences. Missing data will be analysed and, if appropriate, multiple imputations will be considered. Attrition analysis will be conducted using e.g., chi square test and student's t-test to detect differences between those lost to follow up and those retained.

In a stepped wedge trial, results are compared across unexposed and exposed observation periods in the clusters, similar to the control and intervention arm in a parallel cluster trial (K Hemming, Haines, Chilton, Girling, & Lilford, 2015). The primary effect of this study will hence be calculated by comparing the main outcome (propensity to ask questions about abuse) in all clusters pre-intervention with all clusters post-intervention. Both mean difference in reported frequency of asking questions and changes in proportion of participants that report ever having asked questions about abuse will be reported. For the continuous outcome a linear mixed effect model will be used and for the binary outcome a generalised linear mixed effect model. The models will consider repeated measures and include cluster as random effect to determine if the anticipated effect of the model is dependent on the cluster, i.e., unit or clinic. During a stepped wedge trial more and more clusters will gradually transition from unexposed to exposed status, meaning that observation in the exposed status will on average be of a later date than the unexposed observation (K Hemming et al., 2015). This may introduce a bias in the study considering that there may be underlying temporal trends affecting the outcome, e.g., an increasing awareness of elder abuse in society over time. Therefore, both intervention status and time will be included as fixed effects in the models. Also, models will be adjusted for covariates, e.g., background characteristics, significantly associated with the outcome.

[figure not shown]
We propose that the education will work by participants overcoming personal and organizational barriers towards asking older patients questions about abuse. The items in REAGERA-P used to evaluate the effect on the different barriers and facilitators are described in figure 1 and they will be included in linear models (for continuous outcome) and generalised linear models (for binary

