outcomes) to determine the effect of the intervention on these outcomes. If results support the theoretical model, efforts will be made to test if changes in perceived barriers mediate a potential effect of the intervention on the primary outcome, i.e., asking questions about abuse.

[figure not shown]
Data from the medical records will be retrieved for the following periods a) 6 months pre-intervention, b) 0-6 months post intervention and c) 6-12 months post intervention. A linear mixed effect model will be used to investigate changes concerning how many victims are identified pre- and post-intervention at the participating clinics.

In all models, we will strive for parsimony; analysis will therefore be performed to determine which variables to include in multivariate analysis and only covariates that significantly affect the model will be included. Assumptions for models will be assessed graphically and, if needed, bootstrapping will be used to ensure model robustness. Significance level will be set at  $p=0.05$  and results will be reported with 95% confidence intervals.

**Figure 1.** Theoretical model. An illustration of the alignment between learning activities (yellow), learning objective, that is, barriers and facilitators on a personal (green) and organisational (blue) level as well as evaluation (red). EA, elder abuse; REAGERA-P, Responding to Elder Abuse in GERiatric care—Provider questionnaire.

**Figure 2** Design of the study and data collection points. An incomplete stepped wedge trial is planned. All clusters are measured pre-intervention (yellow squares=baseline and in conjunction with the educational day) and post-intervention (blue squares=at 6–8 months and 12–14 months of follow-up). Time of intervention is denoted by the red contour.

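### Aim 1 has one primary effect but two unranked tests of it (ever asked, number of times asked), each at 0.05, and the plan does not say which one decides

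*Combined protocol and SAP*

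**What the plan says.** The Aim section sets one question as aim 1: "Investigate whether the education increases participants' propensity to ask questions about abuse". The main outcome under Measurements is a single self-reported count, from 0 up to a top category of 10 and above, and "The answers will be analysed both as a dichotomous variable (never/ one or more times) and as a continuous variable".

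Statistical analysis speaks of one primary effect: "The primary effect of this study will hence be calculated by comparing the main outcome (propensity to ask questions about abuse", all clusters before against all clusters after the education. It then gives that effect two estimates. "Both mean difference in reported frequency of asking questions and changes in proportion of participants that report ever having asked questions about abuse" are to be reported, and "For the continuous outcome a linear mixed effect model will be used and for the binary outcome a generalised linear mixed effect model". The end of the same section fixes one level for all models ("Significance level will be set at" 0.05) with 95% confidence intervals. It mentions no adjustment, no order of testing, no requirement that both forms succeed, and no rule for results that disagree.

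Sample size uses only the binary form. A proportion "was set as outcome, and we used data from the pilot study to estimate the proportion under control at 0.26", against 0.56 under intervention.

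Two places bear on timing. Study design reports of the first primary care centres that "their first follow up was conducted nine months post intervention", so some follow-up had been collected when this version was written. The Background section (paragraph on Figure 1) and the closing Note trace the statistical analysis text to a protocol paper published in 2022.

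**The concern.** With one primary effect and two unranked tests, the plan does not define what counts as a positive answer to aim 1. If one form reaches p<0.05 and the other does not, three readings fit the text: the education worked because one form shows it, it was not shown to work because both were needed, or the form used for sample size decides. The choice can then be made with the results in view. The first reading gives two chances at 0.05, so the error rate for aim 1 rises above 5%. The second costs power. The third controls the error at 5% but is written nowhere.

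The gap carries forward. The mediation analysis takes asking about abuse as its target without saying in which form.

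**Working it through.** **Inputs from the documents.** Proportions 0.26 and 0.56, significance level 0.05, power 0.8, sufficient cluster size 10, smallest expected cluster 31, cluster autocorrelation 0.6, cluster-size coefficient of variation 0.5 (Sample size); count capped at 10 (Measurements); about 700 participants anticipated (note to Figure 2).

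**Assumptions, not from the documents.** Geometric counts among those who ask, with mean 1.5, 3, 5 or 7 before capping; independent observations; normal test statistics; two-sided tests.

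**Step 1: the plan's own figure.** The cluster size of 10 cannot be confirmed, because the intracluster correlation (ICC), the number of clusters used in the calculation and the sidedness are not stated. In a complete three-step, four-period design with the stated autocorrelation and cluster-size variation, and 9 clusters assumed, 80% power needs size 9 at ICC 0.10 and 11 at ICC 0.15. The stated 10 is therefore plausible.

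**Step 2: no true effect, 26% asking.** Let r be the correlation between ever asked and the capped count, and c = 1.96. Then P(either significant) = 1 − P(|Z1|<c and |Z2|<c), with Z1 and Z2 bivariate normal with correlation r. P(exactly one) = 2 × (P(either) − 0.05).

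| Mean among askers | r | Either form | False claim of increase | Exactly one |
|---|---|---|---|---|
| 1.5 | 0.83 | 7.6% | 3.8% | 5.2% |
| 3 | 0.75 | 8.1% | 4.05% | 6.2% |
| 5 | 0.78 | 7.9% | 3.96% | 5.9% |
| 7 | 0.815 | 7.7% | 3.85% | 5.4% |

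The reference values for one named form are 5% and 2.5%. Negative binomial counts with 74% zeros give r from 0.71 to 0.91 and 6.9-8.3% for either form. Two independent tests would give 1 − 0.95² = 9.75%.

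**Step 3: planned effect true, counts among askers unchanged.** Observations per group for 80% power on the binary form: (1.96 + 0.8416)² × (0.26 × 0.74 + 0.56 × 0.44) / 0.30² = 7.849 × 0.4388 / 0.09 = 38.3. Ranges are over the four means.

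| Observations per group | Relative information | Binary power | Exactly one significant | Binary only | Count only | Both |
|---|---|---|---|---|---|---|
| 38.3 | 1 | 80% | 25-35% | 23-33% | 2% | 47-57% |
| 60 | 1.57 | 94% | 17-27% | 16-26% | 1% | 67-78% |
| 77 | 2.0 | 98% | 11-20% | 10-19% | 0.3% | 79-87% |
| 119 | 3.1 | over 99% | 3-7% | 3-7% | about 0% | 93-97% |

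**Step 4: which row is nearest to the plan.** With 9 clusters, ICC 0.10-0.15, autocorrelation 0.6 and equal cluster sizes (9 clusters, ICC and equal sizes assumed), mean cluster sizes from 31 to 78 (700/9 = 78) give binary power of about 0.94-0.996. That is 1.6-2.7 times the information needed for 80%. The first row is therefore near an upper figure. It is not excluded: a 40% response in a cluster of 31 leaves 0.40 × 31 = 12.4, and the note to Figure 2 reports that one cluster fell to seven.

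**Step 5: when the count is the better form.** Assumed: asking rises from 0.26 to 0.36 and the mean among askers from 1.5 to 3, with 38.3 per group. Power is 16% for the binary form and 50% for the count, and only the count is significant in 36% of trials.

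**The case against.** The best defence has four parts.

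- **Both results are promised.** This stands. A discordant pair cannot be hidden, and a reader who infers selective reporting goes further than the text. What remains open is which result carries the conclusion.
- **The two forms summarise one item.** This stands as a limit on size. In step 2, at least 99% of null trials with exactly one significant form have both estimates on the same side. Correlation reduces the inflation without removing it.
- **The sample size already points to the proportion.** It shows which form was powered and makes a count-only headline easy to notice. It does not say that this form decides, and Measurements and Statistical analysis treat the two as equals.
- **Timing.** A reader might infer from the completed follow-up that the two forms were kept open with results in hand. The documents do not support that. They trace the analysis text to a 2022 publication, and nothing suggests that outcomes were examined before the two forms were chosen. They also do not say whether outcomes had been examined by the time of this version, which is why a dated statement is useful.

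It is also tempting to say that this trial's false-positive rate is 7-8%. That needs a rule that either form suffices, which the plan neither states nor excludes.

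**Conclusion.** The concern holds as an undefined decision rule for aim 1. The omission is plain from the text and does not depend on the calculations; that the level is unadjusted is read from the plan's silence.

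Its size is moderate. If either form may support the claim, the two-sided error is about 7-8% instead of 5%, and a false claim of increase about 4% instead of 2.5%. If the planned effect is true, disagreement is an ordinary outcome: 25-35% of trials at exactly 80% binary power, about 11-27% at 1.6-2 times the information, and less beyond that. The 25-35% should not be read as this trial's expected rate, because the plan's own cluster sizes imply more information. All these figures rest on assumed count distributions and leave out clustering, repeated measures and period effects. They illustrate the rule and are not this trial's error rates. The plan should be changed, but the gap does not invalidate the design.

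**What to change.** Before any post-intervention outcome data are examined, add a dated statement to the SAP, for example:

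*The primary analysis for aim 1 is the dichotomous form (never versus at least once), tested at two-sided 0.05. The number of times asked is a secondary analysis of the same item. It is always reported with its mean difference and 95% confidence interval, and it supports a confirmatory claim only if the primary analysis is significant.*

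If outcome data have already been examined, say so, present both forms together, and make no confirmatory claim based on one alone.

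This takes a few sentences, needs no new data, leaves both results reported, and keeps the form on which the trial was sized. The downside is that a significant count alone could no longer support the main claim. At the planned effect this costs about 2% of trials or fewer. It costs much more if the education mainly makes existing askers ask more often (36% in the assumed example of step 5), so the sponsor should choose deliberately.

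The alternatives cost power at the planned effect. Requiring both forms gives 47-57% where the binary form alone has 80%, and 67-87% at 1.6-2 times the information. Testing each form at 0.025 gives 73-74% in place of 80%.
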